13.0 REGISTRATION GUIDELINES

- 13.1 Patients must be registered prior to initiation of treatment (no more than five working days prior to planned start of treatment).
- 13.2 For either phone or web registration, the individual registering the patient must have completed the appropriate Southwest Oncology Group Registration Form. The completed form must be referred to during the registration but should not be submitted as part of the patient data.

The individual registering the patient must also be prepared to provide the treating institution's name and ID number in order to ensure that the current (within 365 days) date of institutional review board approval for this study has been entered into the data base. Patients will not be registered if the IRB approval date has not been provided or is > 365 days prior to the date of registration.

13.3 Registration procedures

You may register patients from Member, CCOP and approved Affiliate institutions to a therapeutics study using the SWOG Registration program. To access the Registration program go to the SWOG Web site (http://swog.org) and click on the Logon SWOG Members Area link to go to the logon (https://swog.org/visitors/logon.asp). This Web program is available at any time except for periods listed under Down Times. Log on as an Individual User using your SWOG Roster ID Number and individual web user password. Help for the logon process may be found at https://swoq.org/visitors/logonhelp.asp. After you have logged on, click on the Clinical Trials link and then the Patient Reg link to go to the Entry Page for the Patient Registration program. If you are a Registrar at an institution with Internet access you are encouraged to register this way. For new users, the link to a "Starter Kit" of help files may be found by clicking on Starter Kit link at the logon page.

To register a patient the following must be done (in order):

- You are entered into the Southwest Oncology Group Roster and issued a SWOG Roster ID Number,
- 2. You are associated as an investigator or CRA/RN to the institution where a registration is occurring, and
- 3. You are granted permission to use the Patient Registration program at that institution.

For assistance with points 1 and 2 call the SWOG Operations Office at [name]. For point 3 you must contact your Web User Administrator. Each SWOG institution has one or more Web User Administrators who may set up Web Users at their institution and assign permissions and passwords to these users. For other password problems or problems with the Patient Registration program, please e-mail [contact]. Include your name, Roster ID Number, and telephone number, when the problem occurred, and exactly what you were doing.

b. If the Web Reg program is not used, the registration must be done by phone.

Member, Affiliate and CCOP Institutions

Registration by phone of patients from member, affiliate and CCOP institutions must be done through the Southwest Oncology Group Data Operations Center in Seattle by telephoning [name], 6:30 a.m. to 4:00 p.m. Pacific Time, Monday through Friday, excluding holidays.

- For either method of registration, exceptions to Southwest Oncology Group registration policies will not be permitted.
 - a. Patients must meet all eligibility requirements.
 - b. Institutions must be identified as approved for registration.
 - Registrations may not be cancelled.
 - d. Late registrations (after initiation of treatment) will not be accepted.

13.5 Institutions participating through the Cancer Trials Support Unit (CTSU), please refer to Appendix 19.1.

14.0 DATA SUBMISSION SCHEDULE

- 14.1 Data must be submitted according to the protocol requirements for **ALL** patients registered, whether or not assigned treatment is administered, including patients deemed to be ineligible. Patients for whom documentation is inadequate to determine eligibility will generally be deemed ineligible.
- 14.2 Master forms are included in Section 18.0 and (with the exception of the sample consent form and the Registration Form) must be submitted to the Data Operations Center in Seattle. Data from approved SWOG institutions must be submitted on-line via the Web; see Section 14.3a for details. Exceptions to online data submission are patient-completed (e.g. Quality of Life) forms and source documents (e.g. pathology/operative/lab reports).
- 14.3 Data Submission Procedures.
 - a. Southwest Oncology Group institutions must submit data electronically via the Web by using the SWOG CRA Workbench. To access the CRA Workbench, go to the SWOG Web site (http://swog.org) and logon to the Members Area. After you have logged on, click on the *CRA Workbench* link to access the home page for CRA Workbench website. Next, click on the *Data Submission* link and follow the instructions. For new users, the link to a "Starter Kit" of help files may be found by clicking on the **Starter Kit** link at the Members' logon page.

To submit data via the web the following must be done (in order):

- You are entered into the Southwest Oncology Group Roster and issued a SWOG Roster ID Number,
- 2. You are associated as an investigator or CRA/RN at the institution where the patient is being treated or followed, and
- 3. Your Web User Administrator has added you as a web user and has given you the appropriate system permissions to submit data for that institution.

For assistance with points 1 and 2 call the Operations Office at [name]. For point 3, contact your local Web User Administrator (refer to the "Who is my Web User Administrator?" function on the swog.org Members logon page). For other difficulties with the CRA Workbench, please email <code>[contact]</code>.

- If you need to submit data that are not available for online data submission, the only alternative is via facsimile. Should the need for this occur, institutions may submit data via facsimile to [name] or [name] locally. Please do not use cover sheet for faxed data. Please make sure that each page of all faxed data includes the SWOG patient number, study ID, and patient initials.
- c. Institutions participating through the Cancer Trials Support Unit (CTSU), please refer to Appendix 19.1.

14.4 WITHIN 14 DAYS OF REGISTRATION:

Submit copies of the following:

- a. **\$0307** Prestudy Form (Form #20161)
- b. All pre-registration breast cancer pathology reports.
- c. Dental Examination Form (Form #30100)

14.5 DURING TREATMENT AT 6 MONTHS, 1 YEAR, 2 YEARS, AND 3 YEARS:

Submit copies of the following:

- a. **S0307** Treatment Summary Form (Form #31453)
- b. **S0307** Adverse Event Summary Form (Form #22831)
- c. **S0307** Serum Creatinine Reporting Form (Form #60188)

14.6 WITHIN 6 MONTHS OF DISCONTINUATION OF PROTOCOL TREATMENT:

Submit the Dental Examination Form (Form #30100).

14.7 WITHIN 14 DAYS OF DISCONTINUATION OF TREATMENT:

Submit copies of the following:

- a. Off Treatment Notice (Form #8756)
- b. **S0307** Supplementary Off Treatment Form (Form #24801)
- c. Final **\$0307** Treatment Form (Form #31453) for current reporting period
- d. Final **S0307** Adverse Event Summary Form (Form #22831)
- e. **S0307** Serum Creatinine Reporting Form (Form #60188)

14.8 AFTER OFF TREATMENT- EVERY 6 MONTHS UNTIL YEAR 5, AND THEN ANNUALLY UNTIL YEAR 10 OR UNTIL DEATH, WHICHEVER COMES FIRST:

Submit the Follow-Up Form (Form #64587) and S0307 Supplementary Follow-Up Form (Form #36846).

14.9 WITHIN 14 DAYS OF PROGRESSION/RELAPSE:

Submit the following:

- a. Follow-up Form (Form #64587) documenting date, site and method for determining malignancy
- b. **S0307** Supplementary Follow-Up Form (Form #36846)
- c. If patient was still on treatment, final **S0307** Treatment Form (Form #31453) for current reporting period
- d. If patient was still on treatment, final \$0307 Adverse Event Summary Form (Form #22831)

14.10 WITHIN 4 WEEKS OF KNOWLEDGE OF SECOND MALIGNANCY:

Submit the Follow-Up Form (Form #64587) documenting date, site and method of determining malignancy.

14.11 WITHIN 4 WEEKS OF KNOWLEDGE OF OSTEONECROSIS OF THE JAW:

Submit the Osteonecrotic Jaw Lesion Form (Form #52641) (see Section 8.4).

14.12 WITHIN 4 WEEKS OF KNOWLEDGE OF DEATH:

Submit the Notice of Death (Form #49467) documenting death information.

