7.11 Evaluation at the time of recurrence

a. Recurrence of disease must be adequately demonstrated. Suspected recurrence should be biopsied or otherwise confirmed if at all possible. Good medical practice requires biopsy proof of recurrent disease, as such documentation helps avoid the occasional mistake of misidentification of a benign lesion as recurrence or of second primary cancers as recurrence. If biopsy proof of recurrence cannot be obtained, radiologic diagnosis will be allowed at the discretion of the treating physician.

- b. Patients must be restaged at the time of recurrence. All patients with recurrence must have the following studies within 30 days of diagnosis and/or biopsy documentation of recurrence.
 - 1. Nucleotide bone scan, CT of chest and abdomen (MRI, CAT or ultrasound of the liver may be substituted for abdomen CT if desired).
 - 2. For patients experiencing bone pain with other sites of recurrence, plain films will be obtained on the painful sites if the bone scan is negative.
 - 3. For patients with other possibly tumor related symptoms, appropriate radiologic or other studies should be obtained to document the sites of disease.

7.12 Criteria for Removal from Protocol Treatment:

- a. Invasive recurrence of disease or diagnosis of new invasive breast primary. A new diagnosis of ipsilateral or contralateral DCIS without an invasive component is not considered to be a recurrence or a second primary.
- b. Unacceptable toxicity (see Section 8.0).
- c. Greater than 3 months in delay of protocol treatment.
- d. Completion of three years of protocol treatment.
- e. The patient may withdraw from the study at any time for any reason.
- 7.13 All reasons for discontinuation of treatment must be documented on the Off-Treatment Notice.
- 7.14 All patients will be followed until death or for 10 years, whichever is first.

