10.0 CRITERIA FOR EVALUATION AND ENDPOINT DEFINITIONS

- 10.1 Invasive Recurrence: Appearance of any new invasive lesions during or after protocol treatment. Whenever possible recurrences should be documented histologically. A new diagnosis of ipsilateral or contralateral DCIS without an invasive component is not considered to be a recurrence.
- 10.2 Sites of first invasive recurrence: All sites of invasive disease documented within 30 days of first documentation of invasive recurrence.
- 10.3 Disease-Free Survival: Time from date of registration to date of first observation of recurrence or death due to any cause. Patients last known to be alive who have not experienced recurrence of disease are censored at their last contact date.
- 10.4 Overall Survival: Time from date of registration to date of death due to any cause. Patients last known to be alive are censored at their last contact date.
- 10.5 Performance Status: Patients will be graded according to the Zubrod performance status scale.

POINT	DESCRIPTION
0	Fully active, able to carry on all pre-disease performance without restriction.
1	Restricted in physically strenuous activity but ambulatory and able to carry out work of a light or sedentary nature, e.g., light housework, office work.
2	Ambulatory and capable of self-care but unable to carry out any work activities; up and about more than 50% of waking hours.
3	Capable of limited self-care, confined to bed or chair more than 50% of waking hours.
4	Completely disabled; cannot carry on any self-care; totally confined to bed or chair.

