VITAL STATUS						
Vital Status: Alive Dead Date of last contact or death: / / / / /						
If vital status is Dead, complete and submit Notice of Death form.						
DISEASE FOLLOW UP STATUS						
Has the patient had a documented clinical assessment for this cancer (since submission of the previous follow-up form)?						
No Yes If Yes, Date of Last Clinical Assessment: / / / /						
NOTICE OF FIRST RELAPSE OR PROGRESSION						
Has the patient developed a first relapse or progression that has not been previously reported?						
□ No □ Yes If Yes, Date of Relapse or Progression: □ / □ / □ / □						
Site(s) of Relapse or Progression:						
NOTICE OF NEW PRIMARY						
Has a new primary cancer or MDS (myelodysplastic syndrome) been diagnosed that has not been previously reported?						
□ No □ Yes If Yes, Date of Diagnosis: □ / □ / □ / □ □						
New Primary Site:						
NON-PROTOCOL TREATMENT						
Has the patient received any non-protocol cancer therapy (prior to progression/relapse) not previously reported?						
□ No □ Yes If Yes, Date of First Non-Protocol Therapy: □						
Agent Name(s):						
LONG TERM ADVERSE EVENT						
Has the patient experienced (prior to treatment for progression or relapse or a second primary, and prior to non-protocol treatment) any severe (grade ≥ 3) long term toxicity that has not been previously reported?						
No Yes If Yes, Adverse Events and Grades:						
Comments:						

64587

SOUTHWEST ONCOLOGY GROUP

S0307 SUPPLEMENTARY FOLLOW UP FORM	Page 1 of 1				
SWOG Patient ID SWOG Study No. S 0 3 0 7	egistration Step 1				
Patient Initials (L, F M) Date of Patient Visit: /					
Institution / Affiliate Physician					
Participating Group: Group Name/Study No./Patient ID/					
NOTICE OF PROGRESSION - ADJUVANT					
Has the patient been diagnosed with opposite breast cancer since submission of last follow	-up form?				
□ No □ Yes Date of diagnosis: □ / □ / □					
Has the patient been diagnosed with first local-regional recurrence (since submission of last	follow-up form)?				
□ No □ Yes Date of First Local-Regional Progression: □ / □ / □ / □					
Site(s) of First Local-Regional Progression: (select all that apply) Ipsilateral breast Chest wall Axilla Axillary nodes Internal mammary nodes Supraclavicular nodes Infraclavicular nodes					
How was this progression information obtained? Clinical assessment Patient se	elf-report only				

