Has the patient been diagnosed with first distant recurrence/progression (since submission form)?	of last follow-up				
□ No □ Yes Date of First Distant Progression: □ / □ / □					
(select all that apply) Brain Nodes Skir	g/pleura n er Visceral				
If the patient has been previously diagnosed with first distant recurrence/progression a bone, has the patient been diagnosed with a subsequent bone recurrence since submis					
follow-up form? No Yes Date of Subsequent Bone Progression: / / / / / / / / / / / / / / / / / / /]				
How was this progression information obtained? Clinical assessment Patient self-report only					
Has the patient experienced a bone fracture since submission of the last follow-up form? Yes No					
If yes, indicate site: Hip Spine Pelvis Wrist Arm Leg Ankle					
Was the fracture traumatic (from greater than standing height)? Yes No					
Has the patient had osteonecrosis or osteomyelitis of the jaw since submission of the last follow-up form?					
No Yes If yes, submit Osteonecrotic Jaw Lesion Form					
Comments: 6/1/20	708				
(FUS0307)					
	36846				

Page 1 of 1

SOUTHWEST ONCOLOGY GROUP OFF TREATMENT NOTICE

SWOG Patient ID SWOG Study No. S Registration Step						
Patient Initials (L, F M)						
Institution / Affiliate Physician						
Participating Group: Group Name/Study No./Patient ID /						
Systemic Therapy: List regimens, start and end dates. For multidrug regimens, do not list individual drugs separately; end date would be the date all drugs in the regimen were discontinued.						
Surgery: List type of surgery, and in the "end date" column, the date of surgery. Radiation: List sites, start and end dates (inclusive of boosts and implants). All dates are MONTH, DAY, YEAR. Explain any blank fields or blank dates in the Comments section. Place an X in appropriate boxes. Circle AMENDED items in red.						
Treatment Start Date						
Off Treatment Reason (select one): Treatment completed per protocol criteria Medically required, due to toxicity, specify: Patient refused, due to toxicity, specify: Progression or relapse. Sites: Death (submit Notice of Death form) Other, specify: Off Treatment Date Date of completion, progression, death or decision to discontinue therapy: / / /						
Will patient receive further treatment? No Yes, specify: Unknown						
Date of Last Contact (or death): / / /						
Vital Status: Alive Dead (submit Notice of Death form)						
Comments:						

Page 1 of 1

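### Section 14.9 collects recurrence sites by day 14 and asks for no update after the 30-day restaging, so a further non-bone distant or local-regional site can go unrecorded

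*Combined protocol and SAP*

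**What the plan says.** Three sections govern how sites of first recurrence are found, defined and reported.

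- **Reporting (14.9).** The Follow-Up Form and the Supplementary Follow-Up Form are due "WITHIN 14 DAYS OF PROGRESSION/RELAPSE". The Follow-Up Form is to be sent "documenting date, site and method for determining malignancy".
- **Restaging (7.11b).** "All patients with recurrence must have the following studies within 30 days of diagnosis and/or biopsy documentation of recurrence". The studies are a bone scan and CT of chest and abdomen (other liver imaging may replace the abdominal CT).
- **Endpoint (10.2).** Sites of first invasive recurrence are "All sites of invasive disease documented within 30 days of first documentation of invasive recurrence".

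Reporting continues after the event. Section 14.8 requires the same two forms "AFTER OFF TREATMENT- EVERY 6 MONTHS UNTIL YEAR 5, AND THEN ANNUALLY UNTIL YEAR 10 OR UNTIL DEATH, WHICHEVER COMES FIRST", and Section 7.14 adds: "All patients will be followed until death or for 10 years, whichever is first". On those later forms the Follow-Up Form asks: "Has the patient developed a first relapse or progression that has not been previously reported". The Supplementary Follow-Up Form has separate dated items for a first local-regional and a first distant recurrence. For a patient whose earlier distant report did not include bone, it also asks: "has the patient been diagnosed with a subsequent bone recurrence".

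The sites feed objective 1.3 (distribution of first-recurrence sites by arm), the bone comparison in Section 11.7, and the statin hypothesis in Section 2.0, which names liver, bone and brain.

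**The concern.** The forms that carry the site list fall due before the scans that complete it have to be done. A centre that follows 14.9 and 7.11b to the letter can file a list that does not meet the definition in 10.2, and nothing in 14.9 asks for a revised list after restaging. The later scheduled forms ask about first events and later bone, not about further sites belonging to the recurrence already reported.

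At stake is the completeness of the first-recurrence site list. The 30-day windows in 7.11b and 10.2 are also worded with different starting points, so a centre and an analyst could count from different days.

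**Working it through.** The plan states no figure for completeness of site data, so this is mainly a comparison of day counts and form items.

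**Step 1: day counts.** Forms are due by day 14 (14.9). Restaging (7.11b) and the endpoint window (10.2) close at day 30. Days after the due date: 30 − 14 = 16, and 16/30 = 53% of the window.

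**Step 2: what the later forms can recover.** Recurrence ends protocol treatment (7.12a), so these patients move to the 14.8 schedule. For a site found on days 15 to 30:

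| Already reported by day 14 | Found on days 15–30 | Prompt on later forms | Recoverable by date? |
|---|---|---|---|
| Local-regional only | First distant site, bone included | First distant recurrence, dated | Yes |
| Distant only | First local-regional site | First local-regional recurrence, dated | Yes |
| Distant, not bone | Bone | Later bone recurrence, dated | Yes |
| Distant | Further non-bone distant site | None | Only through comments or an ad hoc amendment |
| Local-regional | Further local-regional site | None | Only through comments or an ad hoc amendment |

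The last two rows are the gap. An example is lung reported at day 0 and liver found at day 25. The Follow-Up Form's relapse item does not help, because that relapse has been reported.

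**Step 3: the two clocks.** Let d be the number of days from first diagnosis to biopsy. If biopsy starts the 7.11b clock and the earlier diagnosis starts the 10.2 clock, compliant restaging may end on day 30 + d of the endpoint clock. If both run from the same event, the offset is 0. The documents give no value for d.

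Take a lesion imaged on day 0, biopsied on day 21, with a bone scan on day 45. Counted from biopsy, the scan is on day 45 − 21 = 24, inside both windows. Counted from imaging, it is on day 45, outside both. It meets 7.11b and misses 10.2 only if each section is read with a different start.

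**Step 4: size.** Section 11.7 expects bone as the first site in 4% of patients, and bone is first in 40% of those who become metastatic. With the 5,400 target, 0.04 × 5,400 = 216 and 216/0.40 = 540 metastatic patients. The next inputs would be the share restaged after day 14 and the share of those with a further non-bone site. For local-regional sites the number of such recurrences would also be needed. None of these is in the documents.

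**Step 5: the bone comparison, as context.** Section 11.7 gives 90% power for 0.052 versus 0.028 by marker group (two-sided 0.05), with markers in two-thirds of patients split at the median. The usual formula is

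power = Φ{ [δ√n − 1.96√(2p̄(1 − p̄))] / √(p₁(1 − p₁) + p₂(1 − p₂)) }

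with δ = 0.024 and p̄ = 0.04.

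- n = 4,500 × 2/3 ÷ 2 = 1,500 per group: 91.9%, close to the stated 90%.
- n = 5,400 × 2/3 ÷ 2 = 1,800 per group: 95.7%.

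Suppose bone sites dated inside the window were not merged back, and 5%, 10%, 20% or 30% of bone-first sites were lost equally in both groups. These shares are assumptions, not figures from the plan. Power at 1,800 per group would be 94.7%, 93.6%, 90.6% or 86.4%.

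**The case against.** The strongest reply is that the 14-day form is not the last record. The same forms recur for years, the main categories are separately dated, and 10.2 is defined by date. Assigning a bone date inside 30 days to the first recurrence is ordinary endpoint derivation. If bone was reported first and a visceral site was missed, bone-first status is still right. The Supplementary Off Treatment Form also records the date and result of a bone scan and is to be sent after that scan. This stands. A reader might infer that sites of first recurrence are recorded incompletely in general, or that the bone comparison in 11.7 is undermined. The forms do not support either inference. What is missing for bone is only a written rule for the merge, which neither 11.7 nor the SAP (Appendix 19.4) gives.

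A second reply is that both follow-up forms have comments fields, that other forms in the set provide for amended entries, and that the data centre issues queries (described for CTSU sites in Appendix 19.1). This stands in part. These routes exist, but nothing in the plan triggers them for a further site that no item asks about.

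A third reply concerns the clocks. Section 7.11a treats an unconfirmed lesion as suspected, and 10.1 prefers histology, so biopsy may itself be the first documentation. On that reading the windows coincide, and step 3 shows that the day-45 case is no proof of lost data. What remains is wording that allows two readings.

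One caution is that the distant-site checklist on the Supplementary Follow-Up Form is only partly legible in the available text. Its questions and date fields can be read, and the point rests on those.

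**Conclusion.** The point holds in a limited form. Following 14.9 exactly can leave a site list that falls short of 10.2, and the later forms repair this for bone and for the first site in a new category. They have no dedicated prompt for a further non-bone distant site, or a further local-regional site, found on days 15 to 30 after that category was reported. The consequence is confined to secondary objective 1.3 and the exploratory statin hypothesis for liver and brain. Disease-free survival needs only the first event, so it is unaffected. The rules are the same in every arm, and no bias between arms is claimed.

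The size is unknown. It is tempting to take 53% of the 540 expected metastatic patients and apply a guessed yield of further sites. That would need an even spread of restaging dates and a detection rate that the documents do not give, and it would count bone sites that can be recovered.

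**What to change.** 1. In 14.9, keep the 14-day notice of the event. Add an amended Supplementary Follow-Up Form, due once restaging is complete, listing every site documented in the 10.2 window.
2. In 11.7 or the SAP, state that a later-bone date inside that window counts as a site of first recurrence.
3. For recurrences already reported, query the restaging dates and sites.
4. Reconcile the starting points in 7.11b and 10.2 so that they cannot be read as different clocks.

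The cost is one amended form per recurrence, a one-time data query, and final site data a few weeks later. No patient procedure is added.
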